5.6 Demographic and Other Baseline Characteristics

The following demographic and baseline characteristics will be summarized for patients in the ITT set:

- Age at time of informed consent (in years, as a continuous variable)
- Gender (Male, Female)
- Race (White, Black or African American, Asian, American Indian or Alaska Native, Hawaiian Native or Other Pacific Islander, Unknown)
- Ethnicity (Hispanic or Latino, Not Hispanic or Latino, Not reported, Unknown).
- Weight at screening (in kilograms)
- Baseline cMCS and pMCS
- Baseline IBDQ

- Duration of history of patient's ulcerative colitis.

By-patient listings of demographic data and other baseline characteristics will be provided.

5.7 Medications and Medical History

5.7.1 Prior and Concomitant Medications

Start and stop dates of medications or medical and surgical procedures will be compared to the date of first dose of study drug to allow them to be classified as either Prior or Concomitant. Medications or medical and surgical procedures that start and stop prior to the date of first dose of study drug will be classified as Prior.

If start and/or stop dates of medications or medical and surgical procedures are missing or partial, the dates will be compared as far as possible with the date of first dose of study drug. Medications or medical and surgical procedures will be assumed to be Concomitant, unless there is clear evidence (through comparison of partial dates) to suggest that they started and stopped prior to the first dose of study treatment.

Medications are coded using World Health Organization Drug Dictionary (WHO DD: SEP 2017) summaries showing number of patients and percentage taking each medication will be provided for each preferred medication term. This will be done separately for prior and for concomitant medications.

A by-patient listing of all prior and concomitant medication data will also be provided.

5.7.2 Medical History

Medical history from the screening visit will be summarized. Medical history will be coded using the MedDRA version 20.1. The number and percentage of subjects experiencing at least one such diagnosis will be summarized by the MedDRA system organ class (SOC) and preferred term (PT).

Summary (n, %) may be presented according to MedDRA groups for specific MH analyses.

By subject listings of medical history will be provided.

5.8 Treatment Compliance

The compliance rate will be assessed as:

Compliance Rate (%) is defined as: (Actual Total Volume (mL) / Prescribed Total Volume) x 100, where Actual Total Volume (mL) is defined as the sum of the real volume injected according to

the case report form records and Prescribed Total Volume (mL) is defined as number of total injections x (Weight of the patient in kg x 0.225 ml/Kg)).

If the compliant rate is <80% then the patient is considered as non-compliant to study treatment. Otherwise, the patient will be considered compliant with the study treatment.

A summary of the treatment compliance measures including the number and percentage of compliant and non-compliant patients will be provided.

A by-patient listing of treatment compliance data will be provided.

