3. DESCRIPTION OF DESIGN AND TRIAL POPULATION

3.1 OVERALL TRIAL DESIGN AND PLAN

This will be an open label, multiple dose, multi-centre study to be conducted in around 12-18 centres in 30-40 patients with a diagnosis of moderate to severe active ulcerative colitis, refractory or intolerant to anti-TNF α and/or anti-integrin treatments.

Dose of Neihulizumab will be 9 mg/kg iv. Patients will receive a total of 10 doses on Day 1 (Week 0), Day 8 (Week 1), Day 15 (Week 2), Day 22 (Week 3), Day 29 (Week 4), Day 36 (Week 5), Day 43 (Week 6), Day 50 (Week 7), Day 64 (Week 9) and Day 78 (Week 11). Patients will be followed up on Day 84 (Week 12, End of Treatment, primary endpoint), Day 112 (Week 16), Day 140 (Week 20) and Day 182 (Week 26, End of Study) after the first dose of Neihulizumab.

In some case, patient may be allowed to continue the treatment of study drug in the judgment of the investigator and sponsor medical monitor.

Blood samples for PK determinations will be drawn approximately 15 minutes before dosing and 2 hours post doing at Visits 2, 9 and 11, 15 minutes before doing at Visits 3, 4, 5, 6, 7, 8 and 10, and at Visits 12, 13 and 14. Anti-drug antibodies (ADA) will be determined in all patients before dosing at Visits 2, 6, 10 and at Visits 12-15. Efficacy will be assessed by Mayo Clinic Score (Complete and Partial), endoscopy, biopsy, Inflammatory Bowel Disease Questionnaire (IBDQ) and Biomarkers (faecal calprotectin and c-reactive protein). Safety will be assessed by adverse event (AE) monitoring, laboratory tests, vital signs, physical examinations, discontinuation of treatment due to AE and immunogenicity.

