4. TREATMENTS

4.1 TREATMENTS TO BE ADMINISTERED

The study medication is produced by Boehringer Ingelheim Pharma GmbH & Co. KG.

All doses will be calculated based on mg/kg body weight.

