4.1.1 Identity of AbGenomics' Investigational Product

The characteristics of the study medication are listed below

Substance:	AbGn-168H monoclonal antibody (mAb)
Pharmaceutical form:	Infusion concentrate
Chemical name:	Anti-human CD162 (P-selectin glycoprotein ligand-1; PSGL-1) monoclonal antibody (mAb)
Manufacturer:	Boehringer Ingelheim Pharma GmbH & Co. KG
Unit Strength:	Each 2 mL vial contains approximately 1 mL of 40 mg/mL solution
Posology:	Multiple doses
Route of administration:	i.v. (approximately 60 minutes)

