4.2 TREATMENTS SCHEME, DOSING DELAY AND DISCONTINUATION

A total of 10 doses of Neihulizumab at 9 mg/kg will be administered to patients over 12 weeks on Day 1 (Week 0), Day 8 (Week 1), Day 15 (Week 2), Day 22 (Week 3), Day 29 (Week 4), Day 36 (Week 5), Day 43 (Week 6), Day 50 (Week 7), Day 64 (Week 9), and Day 78 (Week 11). Neihulizumab will be administered intravenously in a total volume of approximately 100 mL over about 1 hour (60 minutes) at a rate of approximately 1.6 to 1.7 mL/min. See [Appendix 10.1](#) for the detailed procedures for preparing Neihulizumab for intravenously administration.

Dosing delay

After the initial infusion, subsequent Neihulizumab infusions can be delayed up to 10 days period due to reversible medical conditions or adverse events or any other reason. If a grade 3 -5 adverse event attributable to the study drug (probably, or definitely related) is observed, additional doses for that patient will be held until the adverse event has returned to baseline. After the adverse reaction is resolved or stabilized, dosing may be restarted if continued

treatment is determined appropriate by the investigator. (unless the adverse reaction is a grade 3 to 5 cytokine release or hypersensitivity reaction, see *Treatment discontinuation* below).

Treatment discontinuation (see also [4.3 Concomitant Therapy and Restrictions](#) and [5.2.2.3 Adverse event and serious adverse event monitoring and reporting](#))

Any patient who experiences a grade 3 to 5 cytokine release or hypersensitivity reaction will be permanently discontinued from Neihulizumab, and withdrawn from the treatment portion of the study. Patients with unambiguous evidence of progression may discontinue Neihulizumab treatment and receive additional therapy per standard institutional guidelines.

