10. APPENDICES

10.1 PROCEDURES FOR PREPARING NEIHULIZUMAB FOR INTRAVENOUS ADMINISTRATION

All steps will be done at room temperature.

Have IV infusion set ready: IV tubing must be able to be used with appropriate infusion pump to precisely control flow rate (NOTE: flow rate for all groups will be fixed at 1.67 mL/min).

Proximal end of IV infusion tubing is inserted into appropriate portion of 100 mL IV infusion bag of normal saline (0.9% NaCl). Distal end of IV infusion set is inserted into the tubing end of a 25G x 3/4 inch butterfly infusion set. An infusion set of similar size can be used as long as the infusion rate can be controlled at 1.67 mL/min.

Note that throughout the following preparation procedures the maximum holding time at each step should not exceed 10 min except the time between preparation and administration to the patient which should not exceed 90 min. Preparation will be done under aseptic conditions.

Required items for preparation (refer to the respective dosing sections below for quantities):

- Vial(s) of AbGn-168H (concentration of antibody in stock solution is 40 mg/mL)
 - Standard 10 mL syringe (BD 300912 or equivalent)
 - #20 gauge needle (Braun 4657500 or equivalent)
 - IV tubing (non-DEHP, 0.2 micron filter i.e Paclitaxel 2C7558 or equivalent)
 - IV infusion bag of 100 mL normal saline (Braun S8004-5264 non-DEHP or equivalent).
 - 25G x 3/4 inch butterfly infusion set (Exel International 26708 or equivalent/similar)
1. Use a 10 ml syringe with #20 gauge needle attached to remove appropriate amount of saline solution from the 100 mL 0.9% NaCl (normal saline) bag according in the patient's weight in kg, as shown in the following table. Discard the removed saline.
 2. Inject the required volume of AbGn-168H, as shown in the table above into the reduced 100 mL saline bag and mix gently. Syringes to be used here are the same type as those for removing saline solution from the 0.9% saline.
 3. Within 90 minutes of starting the preparation, start the infusion of the saline solution at 1.6-1.7 mL/min, for a total of approximately 100 mL over about 1 hr (60 minutes).

9 mg/kg Neihulizumab dosing table

Weight (Kg/lb)				Volume of saline to be withdrawn out of saline bag	Volume of Neihulizumab to be injected into saline bag
at least		and less than			
Kg	lb	Kg	lb	(mL)	(mL)
40	88.2	45	99.2	9	9
45	99.2	50	110.2	10.1	10.1
50	110.2	55	121.3	11.3	11.3
55	121.3	60	132.3	12.4	12.4
60	132.3	65	143.3	13.5	13.5
65	143.3	70	154.3	14.6	14.6

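### The SAP's prescribed volume is not the volume sites are told to inject, so a fully and correctly dosed patient scores 88.9–100.4% on compliance, not 100% (minor effect)

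*SAP*

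**What the plan says.** Protocol 3.1 and 4.2 give the dose: "Dose of Neihulizumab will be 9 mg/kg iv" and "A total of 10 doses of Neihulizumab at 9 mg/kg will be administered to patients over 12 weeks". Protocol 4.1 adds: "All doses will be calculated based on mg/kg body weight". The drug concentration comes from Protocol 4.1.1: "Each 2 mL vial contains approximately 1 mL of 40 mg/mL solution".

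Sites prepare each infusion from Protocol Appendix 10.1: "Inject the required volume of AbGn-168H, as shown in the table above into the reduced 100 mL saline bag". The table is titled "9 mg/kg Neihulizumab dosing table" and prints one volume for each 5-kg band from 40 to 140 kg.

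SAP 5.8 defines the compliance rate as actual total volume over prescribed total volume, as a percentage. The numerator is the sum of volumes recorded on the case report form. For the denominator, "Prescribed Total Volume (mL) is defined as number of total injections x (Weight of the patient in kg x 0.225 ml/Kg". The cut is: "If the compliant rate is <80% then the patient is considered as non-compliant to study treatment". The result goes into one summary and one listing.

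SAP 5.10.1 plans a by-patient listing of days and total mg. Protocol 7.1 and SAP 5.5.1 also promise a summary of study drug dosing, without saying what it will contain.

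**The concern.** A compliance rate should read 100% when the site does exactly what it was told. Here the denominator uses unbanded weight, while the instruction to sites is banded and rounded down to the lower edge of each band. The rate therefore mixes a built-in shortfall with missed or incomplete infusions, and a reader cannot separate the two.

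The SAP also does not say whether its injection count means infusions given or infusions planned. If given, the rate cannot detect a missed infusion at all. If planned, the banding shortfall can push a patient near the cut below 80%.

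The reported description of the regimen is also affected, since the nominal 9 mg/kg is reached only near the lower edge of each band.

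**Working it through.** **Inputs.** Dose 9 mg/kg (Protocol 3.1, 4.2); concentration 40 mg/mL (Protocol 4.1.1, Appendix 10.1); 20 table rows (Appendix 10.1); factor 0.225 mL/kg and cut 80% (SAP 5.8); 10 planned doses under Amendment 4 and 8 under Amendments 1–3 (SAP 4.1).

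**The SAP factor reproduces.** 9 mg/kg ÷ 40 mg/mL = 0.225 mL/kg.

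**The table follows the lower edge.** For every row I took table volume − 0.225 × lower edge. For example, 40 kg: 9 − 9.000 = 0; 50 kg: 11.3 − 11.250 = +0.05; 65 kg: 14.6 − 14.625 = −0.025; 135 kg: 30.4 − 30.375 = +0.025. All 20 differences lie between −0.025 and +0.05 mL, which is rounding to 0.1 mL.

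**Delivered dose and score, all infusions given.** Dose = volume × 40 ÷ weight. Score = volume ÷ (0.225 × weight).

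| Band (kg) | Volume (mL) | mg/kg at lower edge | mg/kg towards upper edge | Band average | Score, lower → upper edge |
|---|---|---|---|---|---|
| 40–45 | 9.0 | 9.00 | 8.00 | 8.48 | 100.0 → 88.9% |
| 50–55 | 11.3 | 9.04 | 8.22 | 8.62 | 100.4 → 91.3% |
| 60–65 | 13.5 | 9.00 | 8.31 | 8.65 | 100.0 → 92.3% |
| 75–80 | 16.9 | 9.01 | 8.45 | 8.73 | 100.1 → 93.9% |
| 95–100 | 21.4 | 9.01 | 8.56 | 8.78 | 100.1 → 95.1% |
| 135–140 | 30.4 | 9.01 | 8.69 | 8.84 | 100.1 → 96.5% |

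Example: at 84 kg the table gives 18 mL. The SAP prescribes 0.225 × 84 = 18.9 mL. The score is 18 ÷ 18.9 = 95.2%, and the dose is 18 × 40 ÷ 84 = 8.57 mg/kg.

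**Averages.** The documents give no weight distribution. I assumed normal weights restricted to 40–140 kg and obtained the averages by simulation.

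| Assumed mean/SD (kg) | Mean mg/kg | Mean score, all given | Mean score, 8 of 10 (planned count) | 7 of 8 scoring below 80% (planned count) |
|---|---|---|---|---|
| 70/15 | 8.68 | 96.4% | 77.1% | 1.9% |
| 80/18 | 8.71 | 96.8% | 77.5% | 0.9% |
| 90/22 | 8.74 | 97.1% | 77.7% | 0.6% |

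Under each assumption about 98% of patients receive less than 9 mg/kg. Widening to mean weights of 60–100 kg (SD 10–20) gives mean scores of 95.9–97.5%.

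**Effect at the 80% cut.**
- All infusions given: the lowest score is 9 ÷ (0.225 × 45) = 88.9%, so nobody crosses.
- Count means infusions given: missed infusions leave both numerator and denominator, so banding again moves nobody across the cut.
- Count means planned, 9 of 10: the lower limit is 0.9 × 88.9% = 80.0%, so nobody falls below.
- Count means planned, 8 of 10: 0.8 × score is below 80% whenever the all-given score is below 100%, which is about 98% of the assumed weights.
- Count means planned, 7 of 8: this falls below 80% only where the score is under 80 ÷ 87.5 = 91.4%, that is at 43.75–45, 49.1–50 and 54.93–55 kg.

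**The case against.** The best defence is that the protocol dose is 9 mg/kg, and measuring delivered volume against that dose is legitimate. If the count means infusions given, the SAP rate × 9 is itself the delivered mg/kg (96.8% × 9 = 8.71), so the present formula already shows the shortfall. That is true, but it makes the figure a measure of dose intensity and not of compliance. On that reading it also cannot register a missed infusion.

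It is also fair that the averages rest on assumed weights. Only the ranges of 8.0–9.04 mg/kg and 88.9–100.4% follow from the documents alone.

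A reader might infer several stronger points that the documents do not support:
- **That the protocol contradicts itself or patients were misdosed.** The bands are printed openly, and a banded table is compatible with dosing calculated on body weight.
- **That efficacy is biased.** The primary analysis (SAP 5.9.2) is a proportion with an exact interval on the mITT set and does not use dose. Nothing in the documents links a shortfall of about 3% to response.
- **That fully dosed patients are called non-compliant.** None can score below 88.9%.
- **That delivered mg/kg would go unreported.** The planned dosing summary could include it; its content is simply unspecified.

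**Conclusion.** The mismatch is real and can be verified row by row: the SAP's prescribed volume is not the volume the protocol instructs sites to inject. As written, the rule misreports compliance for correctly dosed patients, by about 3–4 percentage points on average and by up to 11.1 (100 − 88.9).

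The consequence is small. SAP 5.5.1 defines no per-protocol set, and no efficacy estimate, analysis set or fully dosed patient's classification changes. The Protocol Deviation Specification named in SAP 5.4.2 is not among the documents, and nothing in them says that it uses this rate. The one material change of label, for exactly 8 of 10 doses, arises only if the injection count means planned infusions.

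The averages assume mean weights of 70–90 kg. Figures for Amendments 1–3 assume the same dosing table, because only the Amendment 4 appendix is available. Low priority, but worth correcting because it costs little.

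**What to change.** 1. In SAP 5.8, define the prescribed total volume as the sum, over planned infusions (10 under Amendment 4, 8 under Amendments 1–3), of the dosing-table volume for the patient's weight band. Outside 40–140 kg, which the table does not cover, use 0.225 mL/kg × weight. State which weight applies: the weight at that infusion, or the latest available if the infusion was missed. Confirm which table was used under Amendments 1–3. The rate then reads 100% for correct dosing and falls only for missed or incomplete infusions. Eight of 10 scores 80.0% and stays compliant if the recorded volumes equal the table volumes and the weight band is unchanged; any small recorded shortfall would still take it below the cut.
2. In the planned dosing summary or SAP 5.10.1, report delivered mg/kg per infusion (volume × 40 ÷ weight) by amendment group. This keeps the banding information that step 1 removes from the compliance rate.
3. In the report, describe the regimen as nominal 9 mg/kg and state the delivered mean.

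The cost is one changed definition, one more summary and one sentence, all from volumes and weights already planned for collection (Protocol 6.1.2 lists weight at each infusion visit). The downside is a slightly lower stated dose.

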5.9 Efficacy Evaluation

5.9.1 Analysis and Data Conventions

5.9.1.1 Handling missing data for Efficacy

All missing values will be treated as a non-responder for primary and secondary binary endpoints. A supportive analysis will be performed using only observed data for the primary and secondary binary endpoints. The primary imputation method for any missing data for continuous variable for secondary efficacy endpoints will be the last observation carried forward (LOCF) approach.

If percentage of missing values at Week 12 and 26 is above 10% overall, then multiple imputation analysis will be performed.

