4.3.2 Restricted Medications

The medications (or classes of medication) listed in Table 4.3.2: 1 must not be taken for the specified times before treatment and for the whole duration of the study. If patients take restricted medications due to experiencing an intolerable increase of UC disease activity according to the investigator's judgment, patients will have to be withdrawn from the trial after the use of these restricted medications.

Patients taking the restricted medications of biologics, Cyclosporine/Tacrolimus or investigational products for medical reasons other than UC will also need to be withdrawn from the trial.

Table 4.3.2:1 Restricted medications

- Any biologics, including anti-TNF α , anti-integrin and anti-IL23 antibodies	8 weeks before D1 dosing and during the whole trial duration
- Tofacitinib or other JAK inhibitors	2 weeks before D1 dosing and during the whole trial duration
- Cyclosporine, Tacrolimus	4 weeks before D1 dosing and during the whole trial duration.

- Rectal corticosteroids or rectal 5-aminosalicylic acid preparations	2 weeks before D1 dosing and during the whole trial duration
- Antibiotics	Oral antibiotics: 4 weeks before D1 dosing; intravenous antibiotics: 8 weeks before D1 dosing; all antibiotics during the whole trial duration
- Investigational products	1 year prior to and during the whole trial duration
- Nonsteroidal anti-inflammatory drugs (NSAIDs)	4 weeks before D1 dosing and during the whole trial duration
- Opiates/Methadone	During the whole trial duration

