4.2 Endpoints

4.2.1 Efficacy Variables

Efficacy will be assessed by cMCS, pMCS, endoscopy, biopsy, Inflammatory Bowel Disease Questionnaire (IBDQ), and Biomarkers (faecal calprotectin and c-reactive protein).

The **primary efficacy endpoint** is proportion of clinical responders at Week 12.

The clinical responder is defined as a \geq 3-point reduction in MCS, a 30% or greater decrease from the baseline score, and with a 1-point or greater decrease of the rectal bleeding subscale or an absolute rectal bleeding score of 0 or 1 at Week 12.

Secondary efficacy endpoints are:

1. The proportion of patients with clinical response at Weeks 6, 7, 9 and 11 defined as a ≥ 2 -point decrease in pMCS, and with a 1-point or greater decrease of the rectal bleeding subscale or an absolute rectal bleeding score of 0 or 1.
2. The proportion of patients with clinical remission, defined as MCS of 2 or lower (or pMCS of 1 or lower) and no subscore higher than 1 at Weeks 6, 7, 9, 11 and 12.
3. The proportion of responders who remain in clinical response and remission at Weeks 16, 20, and 26.
4. Flexible sigmoidoscopy subscore changes from baseline at Weeks 12 and 26.
5. The proportion of patients with sigmoidoscopic improvement, defined as any decrease in MCS endoscopic subscore, at Week 12 and 26.
6. The proportion of patients with mucosa healing defined as an absolute subscore for endoscopy of 0 or 1 at Weeks 12 and 26.
7. Change of histological activity grade from baseline at Weeks 12 and 26 using the Geboes system.
8. The proportion of patients with histological healing defined as histological grade = 0 at Weeks 12 and 26.
9. Change of Inflammatory Bowel Disease Questionnaire (IBDQ) from baseline at Weeks 12 and 26.
10. The proportion of patients with IBDQ response, defined as an increase from baseline of at least 16 points at Weeks 12 and 26.

Above time points are for the patient enrolled under Protocol Amendment 4. The time points for the patient enrolled under Amendments 1-3 are given in the table in the SAP section 4.5.2 as well as in Appendix 1 'Schedule of Assessments (Protocol Amendment 1-3)' and Appendix 2 'Schedule of Assessments (Protocol Amendment 4)'.

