5.9.3 Secondary Efficacy Endpoints

The secondary endpoints (1, 2, 3, 5, 6, 8, 10) of clinical outcomes listed in Section 3.2.1 will be summarized with frequencies and percentages along with 2-sided 95% exact Clopper-Pearson confidence interval at given weeks.

The changes from baseline of secondary endpoints (4,7,9) including total score of IBDQ at Weeks 12 and 26 will be analysed separately using Analysis of Covariance model (ANCOVA) with baseline value as covariate. The descriptive statistics and the absolute change from baseline will be presented for each time point. Least square means and 95% confidence interval (CI) will also be provided at each assessment time point.

The estimated proportion of primary and secondary end points and 95% CI at each week will be displayed graphically using line graph. A line plots showing the mean change and 95% CI from baseline vs. time in weeks for secondary endpoints will be produced for mITT population.

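### LOCF as the primary method for endpoints 4, 7 and 9 carries the end-of-treatment value to Week 26 for patients with nothing measured later, while the paired binary endpoints count the same patients as failures

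*SAP*

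**What the plan says.** SAP 5.9.1.1 has different rules for the two kinds of outcome. For missing continuous values, the primary method "for secondary efficacy endpoints will be the last observation carried forward (LOCF) approach". For binary ones: "All missing values will be treated as a non-responder for primary and secondary binary endpoints".

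Two further sentences in that section matter. "A supportive analysis will be performed using only observed data for the primary and secondary binary endpoints"; the continuous endpoints are not included. And "If percentage of missing values at Week 12 and 26 is above 10% overall, then multiple imputation analysis will be performed"; no imputation model is given, and nothing says whether the result replaces LOCF or stands beside it.

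SAP 5.9.3 names the continuous endpoints: "The changes from baseline of secondary endpoints (4,7,9) including total score of IBDQ at Weeks 12 and 26" go to ANCOVA with the baseline value as covariate. Endpoint 4 in SAP 4.2.1 is "Flexible sigmoidoscopy subscore changes from baseline at Weeks 12 and 26". Endpoints 7 (Geboes grade) and 9 (IBDQ) use the same weeks. Their binary partners at those weeks are endpoints 5 and 6 (endoscopic subscore), 8 (histology) and 10 (IBDQ).

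The schedules (protocol Table 1; SAP Appendices 2 and 3) place sigmoidoscopy, histology and IBDQ at screening, Week 12 and Week 26 only. Weeks 16 and 20 have the partial Mayo score but none of these three.

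Four other provisions bear on the point:

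- Protocol section 7 says that missing data are neither estimated nor carried forward in any analysis.
- Footnote 1 to protocol Table 1 asks that a patient who cannot continue have the end-of-study assessments at the last visit.
- SAP 5.5.2 assigns early-termination assessments to visits by study day.
- Protocol 4.3.2 says of patients who take restricted drugs for an intolerable rise in UC activity that "patients will have to be withdrawn from the trial after the use of these restricted medications".

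**The concern.** Week 12 is the end of treatment. Week 26 follows a planned drug-free period and is where the trial can see whether benefit lasts. Protocol 1.1 presents a long disease-free period as a possible advantage over biologics that must be given continuously. Carrying Week 12 to Week 26 assumes that persistence for every patient to whom it is applied.

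The two rules in SAP 5.9.1.1 also disagree about the same patient. Someone whose endoscopic subscore improved at Week 12 and who has no later endoscopy counts as improved at Week 26 in endpoint 4 and as not improved in endpoint 5. Histology and IBDQ have the same split. A flare recorded on the partial Mayo score at Week 16 or 20 does not correct the carried value, because none of the three measures is scheduled then.

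**Working it through.** The plan states no figure for the effect of LOCF, so there is none to reproduce. Its power statement (SAP 5.14) concerns the primary endpoint and plays no part here.

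**Time since last dose.** Dosing days are from SAP 4.1. Visits are Day 84 (Week 12) and Day 182 (Week 26).

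| Patients | Last dose | To Week 12 | To Week 26 |
|---|---|---|---|
| Amendment 4 | Day 78 | 84 − 78 = 6 days | 182 − 78 = 104 days |
| Amendments 1–3 | Day 71 | 84 − 71 = 13 days | 182 − 71 = 111 days |

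Protocol 1.2 gives a half-life of 132.1 h (5.5 days) at 9 mg/kg in a psoriasis study. On that figure, Week 12 is 1.1 or 2.4 half-lives after the last dose, and Week 26 is 18.9 or 20.2.

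**What LOCF carries to a missing Week 26.**

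- Week 12 present, nothing later: the Week 12 value.
- Exit assessments done, say on Day 120 (Week 16 window, Days 105–132): the exit value, which would show a flare.
- Week 12 also missing: baseline (zero change) or nothing. The SAP does not say which.

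Only the first case builds in persistence.

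**Size.** In a single group, the ANCOVA least-squares mean at the mean baseline equals the mean change. With m of N patients in the first case,

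shift = (m/N) × (Week 12 change − true Week 26 change).

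Assume N = 40 and that each lost patient truly returned to baseline:

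| Lost | IBDQ, 16-point loss each | IBDQ, 30-point loss each | Endoscopy, 1-point loss each |
|---|---|---|---|
| 4 (10%) | 0.10 × 16 = 1.6 | 0.10 × 30 = 3.0 | 0.10 × 1 = 0.10 |
| 8 (20%) | 0.20 × 16 = 3.2 | 0.20 × 30 = 6.0 | 0.20 × 1 = 0.20 |

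All shifts are in the favourable direction. Four of 40 is exactly 10%, which does not exceed the trigger. Multiple imputation starts at 5 of 40 (12.5%) or 4 of 30 (13.3%). SAP 5.2 analyses the two amendment groups separately, so each lost patient weighs more than at N = 40.

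**The two rules side by side.** Assume that 24 of 40 patients improved by one endoscopic point at Week 12 and that 4 of those 24 are lost after returning to baseline. LOCF gives a mean Week 26 improvement of 24/40 = 0.60, where the truth is 20/40 = 0.50. The values behind endpoint 4 imply 60% improved; endpoint 5 reports 50%.

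**Would a repeated-measures model correct it?** Suppose that all 40 patients gain 30 IBDQ points at Week 12, that the 36 who stay still average 30 at Week 26, and that the 4 lost are truly at 0. The true mean is (36 × 30 + 4 × 0)/40 = 27.0. LOCF gives 30.0. A missing-at-random model predicts about 30 for the four, since their Week 12 values resemble those of patients who stayed, so it also gives about 30. The observed mean is 30, with n = 36. Only assigning zero change recovers 27.0.

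**The case against.** The strongest reply is that the plan already contains safeguards. Patients who leave are to have the end-of-study assessments at their last visit, and these are slotted by study day, so LOCF would carry the exit value. Patients taken off drug are encouraged to keep attending (protocol 3.3.4.1). Above 10% missing, multiple imputation is performed. Endpoints 4, 7 and 9 are secondary estimates in a single-arm trial, and persistence of response is addressed by endpoint 3 under the stricter non-responder rule.

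Most of this stands and limits the point. A reader might infer that any patient lost after a flare keeps the Week 12 improvement. The documents do not support that: it holds only where the exit assessments are not done. A reader might also infer from protocol 4.3.2 that missing Week 26 data are concentrated in patients who lost benefit. That is plausible but not shown. SAP 4.1 reports early close-out because of COVID-19 and slow enrolment, so some missingness may be administrative. Larger biases, computed at 15% to 40% missing, would all lie above the multiple-imputation trigger, so LOCF would not stand alone there. Nor should a shift in a group mean be read against the 16-point IBDQ threshold, which applies to individual patients.

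The safeguards leave gaps. Exit assessments do not help when a patient simply stops attending. The multiple imputation has no stated model or role, so LOCF remains primary. If it assumes missing at random, it has the same limit as the repeated-measures model above. At or below 10% missing, endpoints 4, 7 and 9 have no alternative analysis.

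**Conclusion.** The concern holds in limited form. For patients with a Week 12 value and no later sigmoidoscopy, biopsy or IBDQ, the primary method assumes at Week 26 the persistence that the visit is meant to examine. It conflicts with the non-responder rule in the same paragraph and with protocol section 7. Neither conflict depends on any assumption about why patients leave.

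The size cannot be taken from the documents, which give no dropout rate. With 4 of 40 lost and full return to baseline assumed, the Week 26 mean is too favourable by 3.0 IBDQ points for a 30-point loss each, or by 0.10 endoscopic points for a 1-point loss each. The off-drug description follows the planned schedule; protocol 3.1 allows continued treatment in some cases. The primary endpoint is unaffected. The SAP should be corrected, but this does not threaten the trial's main result.

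**What to change.** Remove LOCF as the primary method for endpoints 4, 7 and 9, which brings the SAP into line with protocol section 7. In its place:

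1. Report observed Week 12 and Week 26 changes with the number observed at each visit. A repeated-measures model is acceptable, but the text should not present it as correcting for loss after a flare.
2. Beside it, report an analysis giving zero change at Week 26 to patients who left after UC worsening or restricted medication, to match the non-responder rule.
3. Keep LOCF at most as a sensitivity analysis.
4. If multiple imputation is kept, state its model and its role.

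Exit values slotted to Week 16 or 20 would no longer reach the Week 26 row, so list them separately.

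The cost is SAP wording and one or two standard analyses, with no new data. Week 26 estimates may be less favourable and their intervals wider.
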